12.6. Appendix 6: Liver Safety Required Actions and Follow-up Assessments

Phase I liver chemistry stopping criteria and required follow-up assessments

Liver Chemistry Stopping Criteria	
ALT-absolute	
ALT \geq 3xULN
 
If ALT \geq 3xULN AND bilirubin^{1,2} \geq 2xULN (> 35% direct bilirubin) or INR > 1.5, Report as an SAE.
 
See additional Actions and Follow-Up Assessments listed below

Required Actions and Follow-up Assessments	
Actions	Follow-Up Assessments

 Report the event to GSK within 24 hrs Complete the liver event CRF, and complete an SAE data collection tool if the event also meets the criteria for an SAE² Perform liver event follow-up assessments Monitor the subject until liver chemistries resolve, stabilise, or return to within baseline (see MONITORING below) 
MONITORING:
 
If ALT \geq 3xULN AND bilirubin \geq 2xULN or INR > 1.5
 
 Repeat liver chemistries (include ALT, AST, alkaline phosphatase, bilirubin) and perform liver event follow-up assessments within 24 hrs Monitor subjects twice weekly until liver chemistries resolve, stabilise or return to within baseline A specialist or hepatology consultation is recommended 
If ALT \geq 3xULN AND bilirubin < 2xULN and INR \leq 1.5:
 
 Repeat liver chemistries (include ALT, AST, alkaline phosphatase, bilirubin) and perform liver event follow-up assessments within 24-72 hrs 	
 Viral hepatitis serology³ Obtain INR and recheck with each liver chemistry assessment until the transaminases values show downward trend Obtain blood sample for PK analysis, obtained within 24 hrs of the dose Serum creatine phosphokinase (CPK) and lactate dehydrogenase (LDH) Fractionate bilirubin, if total bilirubin \geq 2xULN Obtain complete blood count with differential to assess eosinophilia Record the appearance or worsening of clinical symptoms of liver injury, or hypersensitivity, on the AE report form Record use of concomitant medications on the concomitant medications report form including acetaminophen, herbal remedies, other over the counter medications Record alcohol use on the liver event alcohol intake case report form 
If ALT \geq 3xULN AND bilirubin \geq 2xULN or INR > 1.5:
 
 Anti-nuclear antibody, anti-smooth muscle antibody, Type 1 anti-liver kidney

Liver Chemistry Stopping Criteria	

 • Monitor subjects weekly until liver chemistries resolve, stabilize or return to within baseline 	
microsomal antibodies, and quantitative total immunoglobulin G (IgG) or gamma globulins
 
 • Serum acetaminophen adduct high performance liquid chromatography (HPLC) assay (quantifies potential acetaminophen contribution to liver injury in subjects with definite or likely acetaminophen use in the preceding week [James LP, 2009]) • Liver imaging (ultrasound, magnetic resonance, or computerised tomography) and/or liver biopsy to evaluate liver disease; complete Liver Imaging and/or Liver Biopsy CRF forms

1. Serum bilirubin fractionation should be performed if testing is available. If serum bilirubin fractionation is not immediately available, discontinue study treatment for that subject if ALT \geq 3xULN and bilirubin \geq 2xULN. Additionally, if serum bilirubin fractionation testing is unavailable, record presence of detectable urinary bilirubin on dipstick, indicating direct bilirubin elevations and suggesting liver injury.
2. All events of ALT \geq 3xULN and bilirubin \geq 2xULN (> 35% direct bilirubin) or ALT \geq 3xULN and INR > 1.5, if INR measured, which may indicate severe liver injury (possible 'Hy's Law'), must be reported as an SAE (excluding studies of hepatic impairment or cirrhosis); INR measurement is not required and the threshold value stated will not apply to subjects receiving anticoagulants.
3. Includes: Hepatitis A IgM antibody; Hepatitis B surface antigen and Hepatitis B Core Antibody (IgM); Hepatitis C RNA; Cytomegalovirus IgM antibody; Epstein-Barr viral capsid antigen IgM antibody (or if unavailable, obtain heterophile antibody or monospot testing); Hepatitis E IgM antibody.

References

12.7. Appendix 7: Country-specific requirements

Not applicable.

12.8. Appendix 8: Protocol Amendment History

Not applicable.

1. REPORTING & ANALYSIS PLAN SYNPOSIS

Overview	Key Elements of the RAP	
Purpose	The purpose of this RAP is to describe the planned analyses and output to be included in the Clinical Study Report for Protocol 204678.	
Protocol	• This RAP is based on the original protocol Dated:19/JUL/2017 of study204678 (GSK Document Number.: 2017N318316_00).	
Primary Objective	• To investigate PK following a single oral dose of Pyrimethamine 50 mg in fasted healthy Japanese male subjects.	
Primary Endpoint	• Cmax, AUC(0-t), AUC(0-inf), AUC(0-24), tmax, t1/2, CL/F, Vd/F from the plasma concentrations of Pyrimethamine in healthy Japanese male subjects, as data permit.	
Study Design	This study will be a single centre, open-label, parallel-group, single oral dose study to evaluate the pharmacokinetic (PK), safety and tolerability of Pyrimethamine in healthy Japanese and Caucasian male subjects.	
	• Sufficient Japanese and Caucasian healthy male volunteer subjects will be enrolled such that 6 subjects of each population complete dosing and critical assessments.	
Analysis Populations	Screened: Consisting of all participants screened in the study.	
	• Screening Failure: Participants who sign the ICF in the study but are never subsequently administered study treatment.	
	Safety: All participants who take at least one dose of study treatment.	
	Pharmacokinetic: This population is defined as all participants administered at least one dose of study treatment and who have PK sample taken and analyzed.	
Hypothesis	• The objectives of this study are to evaluate safety and tolerability of Pyrimethamine and to estimate Pyrimethamine pharmacokinetic parameters in healthy male Japanese and Caucasian subjects. No formal statistical hypotheses will be tested. Descriptive statistics will be used to assess safety and tolerability objectives. An estimation approach will be used to address the pharmacokinetic study objectives, where point estimates and corresponding 95% confidence intervals will be constructed, unless otherwise stated.	

Overview	Key Elements of the RAP
Pharmacokinetic Analyses	• Individual Pyrimethamine plasma concentration-time profiles (by group, and subject) and median/mean (±SD) profiles by group will be plotted and listed.
	• Plasma concentration time data for Pyrimethamine will be analyzed by non-compartmental methods using Phoenix WinNonlin (version 6.3 or higher) and all derived PK parameters will be graphically presented, summarised and listed. No formal statistical analyses will be conducted.
Safety Analyses	Safety data will be presented in tabular and/or graphical format and summarised descriptively.

1.1. History

Version	Issue Date	Amendments	Reason
00	15-SEP-2017	Original (New document)	-

2. SUMMARY OF KEY PROTOCOL INFORMATION

2.1. Changes to the Protocol Defined Statistical Analysis Plan

There were no changes or deviations to the originally planned statistical analysis specified in the protocol (Dated: 19/JUL/2017).

2.2. Study Objective(s) and Endpoint(s)

Objectives	Endpoints
Primary Objectives	Primary Endpoints
To investigate PK following single dose of Pyrimethamine 50 mg in fasted status in healthy Japanese male subjects.	Cmax, AUC(0-t), AUC(0-inf), AUC(0-24), tmax, t1/2, CL/F, Vd/F of the plasma concentration of Pyrimethamine in healthy Japanese male subjects, as data permit.
Secondary Objectives	Secondary Endpoint
To investigate PK following single dose of Pyrimethamine 50 mg in fasted status in healthy Caucasian male subjects.	Cmax, AUC(0-t), AUC(0-inf), AUC(0-24), tmax, t1/2, CL/F, Vd/F of the plasma concentration of Pyrimethamine in healthy Caucasian male subjects, as data permit.
To assess safety and tolerability following single dose of Pyrimethamine in fasted status in healthy Japanese and Caucasian male subjects.	AE and change from the baseline of clinical laboratory values, vital signs and ECG.

2.3. Study Design

Overview of S	Overview of Study Design and Key Features		
Design Features	This study will be a single centre, open-label, parallel-group, single oral dose study to evaluate the PK, safety and tolerability of Pyrimethamine in healthy male Japanese and Caucasian subjects.		
Dosing	 Subjects will have a screening visit within 30 days prior to the first dose of study treatment, one treatment period, and re-visits 15 (±1) and 22 (±1) days after the dose for follow-up assessments including PK sampling. Subjects will be housed in the Clinical Research Unit from Day -1 through Day 8, and return to the unit on Day 15 (±1) and 22 (±1) for the remaining PK samples and safety assessments post dose. During the treatment period, subjects will receive single dose of Pyrimethamine 50 mg in the fasted state after overnight fast (at least 10 hours). Calcium folinate 15 mg will be coadministered with Pyrimethamine at Day 1, and will continue to be administered once a day until Day 8. Blood sampling for PK analysis and safety assessments will be performed prior to dosing and over 22 days after dosing. The duration of each subject's participation will be approximately 2 months from screening to the follow-up. 		
Treatment Assignment	 Sufficient Japanese and Caucasian healthy male subjects will be enrolled such that 6 subjects of each population complete dosing and critical assessments. 		
Interim Analysis	No interim analyses will be planned.		

2.4. Statistical Hypotheses

The objectives of this study are to evaluate safety and tolerability of Pyrimethamine and to estimate Pyrimethamine pharmacokinetic parameters in healthy Japanese and Caucasian male subjects. No formal statistical hypotheses will be tested. Descriptive statistics will be used to assess safety and tolerability objectives by group (Japanese, Caucasian). An estimation approach will be used to address the pharmacokinetic study objectives, where point estimates and corresponding 95% confidence intervals will be constructed, unless otherwise stated.

3. PLANNED ANALYSES

3.1. Interim Analyses

An interim analysis is not planned.

3.2. Final Analyses

The final planned primary analyses will be performed after the completion of the following sequential steps:

- 1. All subjects have completed the study as defined in the protocol.
- 2. All required database cleaning activities have been completed and final database release and database freeze has been declared by Data Management.
- 3. Even though single arm study, randomisation codes have been distributed according to RandAll NG procedures.

4. ANALYSIS POPULATIONS

Population	Definition / Criteria	Analyses Evaluated
Screened	Consisting of all participants screened in the study	Study Population
Screening Failure	Participants who sign the ICF in the study but are never subsequently administered study treatment. All participants who sign the ICF have the screening test in the study.	Study Population
Safety	All participants who take at least one dose of study treatment.	Study PopulationSafety
Pharmacokinetic	This population is defined as all participants administered at least one dose of study treatment and who have PK sample taken and analysed.	• PK

4.1. Protocol Deviations

- Important protocol deviations (including deviations related to study inclusion/exclusion criteria, conduct of the trial, patient management or patient assessment) will be summarised and listed.
- Protocol deviations will be tracked by the study team throughout the conduct of the study in accordance with the Protocol Deviation Management Plan.
 - Data will be reviewed prior to freezing the database to ensure all important deviations and deviations which may lead to exclusion from the analysis are captured and categorised on the protocol deviations dataset.
 - This dataset will be the basis for the summaries and listings of protocol deviations.
- A separate listing of all inclusion/exclusion criteria deviations will also be provided. This will be based on data as recorded on the inclusion/exclusion page of the eCRF.

5. CONSIDERATIONS FOR DATA ANALYSES AND DATA HANDLING CONVENTIONS

Table 1 provides an overview of appendices within the RAP for outlining general considerations for data analyses and data handling conventions.

Table 1 Overview of Appendices

Section	Component
10.1	Appendix 1: Protocol Deviation Management
10.2	Appendix 2: Time & Events
10.3	Appendix 3: Treatment States and Phases
10.4	Appendix 4: Data Display Standards & Handling Conventions
10.5	Appendix 5: Derived and Transformed Data
10.6	Appendix 6: Premature Withdrawals & Handling of Missing Data
10.7	Appendix 7: Values of Potential Clinical Importance

6. STUDY POPULATION ANALYSES

6.1. Overview of Planned Analyses

The study population analyses will be based on the Safety population, unless otherwise specified.

Table 2 provides an overview of the planned study population analyses, with full details of data displays being presented in Appendix 9: List of Data Displays.

 Table 2
 Overview of Planned Study Population Analyses

Display Type	Data	Displays Gene	rated
	Table	Figure	Listing
Subject Disposition			
Subject Disposition and Reason for Study Withdrawal	Υ		Υ
Screening Status and Reasons for Screen Failure	Y		Υ
Protocol Deviations			
Important Protocol Deviations	Υ		Υ
Subjects with Inclusion/Exclusion Criteria Deviations			Υ
Populations Analysed			
Study Populations	Y		
Subjects Excluded from Any Population			Υ
Demographic and Baseline Characteristics			
Demographic Characteristics	Υ		Υ
Demographic Characteristics for Screening Failure			Υ
Age Ranges	Y		
Race and Racial Combinations	Y		Υ
Race and Racal Combination for Failure			Υ
Medical Conditions and Concomitant Medications			
Medical Conditions			Υ
Concomitant Medications			Y
Exposure and Treatment Compliance			
Exposure to Study Treatment			Υ

NOTES:

• Y = Yes display generated.

7. SAFETY ANALYSES

The safety analyses will be based on the Safety population, unless otherwise specified.

7.1. Overview of Planned Analyses

Table 3 provides an overview of the planned analyses, with further details of data displays being presented in Appendix 9: List of Data Displays.

Table 3 Overview of Planned Safety Analyses

Display Type		Absolute				
	Sur	nmary	Individual			
	Т	F	L			
Adverse Events (AEs)						
All AEs by SOC and PT	Υ		Υ			
All AEs by Maximum Intensity	Υ					
Drug-Related AEs by SOC and PT	Υ					
Drug-Related AEs by Maximum Intensity	Υ					
Subject Numbers for Individual AEs			Υ			
Relationship Between AE SOCs, PT and Verbatim Text			Υ			
Serious and Other Significant AEs						
Serious AEs			Υ			
AEs Leading to Withdrawal from Study			Υ			

NOTES:

- T = Table, F = Figures, L = Listings, Y = Yes display generated, SOC = System Organ Class, PT = Preferred Term.
- Summary = Represents TF related to any summaries (i.e. descriptive statistics) of the observed raw data.
- Individual = Represents FL related to any displays of individual subject observed raw data.

7.2. Overview of Planned Clinical Laboratory Analyses

Table 4 provides an overview of the planned analyses, with further details of data displays being presented in Appendix 9: List of Data Displays.

Table 4 Overview of Planned Clinical Laboratory Analyses

Display Type		Abso	olute	Change from BL			
	Summary Individual			Sumr	nary	Individual	
	Т	F	L	T	F	L	
Chemistry							
Chemistry Data	Υ		Υ	Υ		Υ	
Chemistry Results Relative to Normal Range				Υ			
All Chemistry Data for Subjects with any Value of Potential Clinical Concern/PCI			Y				

Display Type		Abs	olute	Change from BL				
	Sum	mary	Individual	Sumr	nary	Individual		
	Т	F	L	Т	F	L		
Hematology		_						
Hematology Data	Υ		Υ	Υ		Υ		
Hematology Results Relative to Normal Range				Υ				
All Hematology Data for Subjects with any Value of Potential Clinical Concern/PCI			Y					
Urinalysis		_						
Dipstick Data (Glucose, Protein, Blood, Ketones, Bilirubin, Urobilinogen)	Υ		Y*					
Gravity and pH	Υ		Υ					
Hepatobiliary (Liver)		_						
Liver Monitoring/Stopping Event Reporting			Υ					
Medical Conditions for Subjects with Liver Stopping Events			Y					
Substance Use for Subjects with Liver Stopping Events			Y					

NOTES:

- T = Table, F = Figures, L = Listings, Y = Yes display generated, PCI = Potential Clinical Importance
- Summary = Represents TFL related to any summaries (i.e. descriptive statistics) of the observed raw data.
 Individual = Represents FL related to any displays of individual subject observed raw data.

7.3. Overview of Planned Other Safety Analyses

Table 5 provides an overview of the planned analyses, with further details of data displays being presented in Appendix 9: List of Data Displays.

Table 5 Overview of Planned Other Safety Analyses

Display Type		Abs	olute	Change from BL			
	Sum	mary	Individual	Sumn	nary	Individual	
	Т	F	L	T	F	L	
ECG							
ECG Findings	Υ		Υ				
ECG Values	Υ		Υ	Υ		Y	
All ECG Values for Subjects with any Value of PCI			Υ				
Vital Signs							
Vitals Values	Υ		Υ	Υ		Υ	
All Vital Signs for Subjects with any Value of PCI			Υ				

NOTES:

- T = Table, F = Figures, L = Listings, Y = Yes display generated, PCI = Potential Clinical Importance
- Summary = Represents TFL related to any summaries (i.e. descriptive statistics) of the observed raw data.
- Individual = Represents FL related to any displays of individual subject observed raw data.

^{*:} If blood or protein is abnormal, microscopic examination will be included.

8. PHARMACOKINETIC ANALYSES

8.1. Overview of Planned Pharmacokinetic Analyses

The pharmacokinetic (PK) analyses will be based on the Pharmacokinetic population, unless otherwise specified.

Table 6 provides an overview of the planned analyses, with full details being presented in Appendix 9: List of Data Displays.

Table 6 Overview of Planned Pharmacokinetic Analyses

Display Type		Untrans	sformed		Log-Transformed				
	Summary		Individual		Summary		Individual		
	F	Т	F	L	F	Т	F	L	
Plasma Drug Concentrations	Υ [1] [2]	Υ	Υ [1]	Υ					
Derived PK Parameters	Υ	Y		Y		Y			

NOTES:

- T = Table, F = Figures, L = Listings, Y = Yes display generated.
- Summary = Represents TFL related to any summaries (descriptive statistics) of the observed raw data.
- Individual = Represents FL related to any displays of individual subject observed raw data.
- 1. Linear and Semi-Log plots will be created on the same display.
- 2. Separate Mean (± SD) and Median plots will be generated.

8.2. Drug Concentration Measures

Plasma concentrations of Pyrimethamine at each nominal time will be listed and summarised by group. Standard summary statistics will be calculated (i.e. mean, standard deviation, median, minimum and maximum).

Individual plasma concentration-time profiles and median/mean profiles by group will be plotted. Each of the figures will contain one plot on the untransformed scale (i.e. a linear plot) and one plot on the log transformed scale (i.e. log-linear plot).

All individual plasma concentration-time profiles will be plotted. Each of the figures will contain one plot on the untransformed scale (i.e. a linear plot) and one plot on the log transformed scale (i.e. log-linear plot).

Refer to Appendix 4: Data Display Standards & Handling Conventions (Section 10.4.3 Reporting Process & Standards).

8.3. Pharmacokinetic Parameters

8.3.1. Derived Pharmacokinetic Parameters

- Derivation of pharmacokinetic parameters will be performed by, or under the direct auspices of, Clinical Pharmacology & Science Promotion Office, GlaxoSmithKline K.K.
- Refer to Appendix 4: Data Display Standards & Handling Conventions (Section 10.4.3 Reporting Process & Standards).
- The pharmacokinetic parameters will be calculated by non-compartmental analysis using Phoenix WinNonlin (version 6.3 or higher)
- All calculations of non-compartmental parameters will be based on actual sampling times recorded during the study.

Pharmacokinetic parameters described in Table 7 will be determined from plasma Pyrimethamine concentration-time data, as data permits.

Table 7 Derived Pharmacokinetic Parameters

Parameter	Parameter Description
AUC(0-24)	Area under the concentration-time curve will be calculated to fixed nominal time 24 hours after administration (AUC(0-24)), using the combination of linear and logarithmic trapezoidal methods (i.e., Linear Up/Log Down calculation method in Phoenix WinNonlin). If a sampling time deviation occurred at nominal time 24 hours after administration (and 24 < t), AUC(0-24) will be calculated using the concentration at time 24 hours after administration post-dose estimated by the method of interpolation. If nominal time 24 hours after administration > t (or if the concentration at time 24 hours after administration was below the limit of quantification), then the concentration (y) at time 24 hours after administration is estimated using λz and last observed Ct according to the formula: $y = Ct(obser) \times e^{-lambda_z z(24-t)}$ Then the following equation will be used to calculate AUC(0-24) where t is the time of last quantifiable plasma concentration. $AUC(0-24) = AUC(0-t) + AUC(t-24)$
AUC(0-t)	If lambda_z is not estimable, AUC(0-24) is not calculated (when 24 > t). Area under the concentration-time curve from time zero time (pre-dose) to the time of last quantifiable concentration (AUC(0-t)) will be calculated by a combination of linear and logarithmic trapezoidal methods. The linear trapezoidal method will be employed for all incremental trapezoids arising from increasing concentrations and the logarithmic trapezoidal method will be used for those arising from decreasing concentrations (i.e., Linear Up/Log Down calculation method in Phoenix WinNonlinl).
AUC(0-inf)	Area under the concentration-time curve from zero time (pre-dose) extrapolated to infinite time (AUC(0-inf)) will be calculated as follows: AUC(0-inf) = AUC(0-t) + C(t) / lambda_z
%AUCex	The percentage of AUC (0-∞) obtained by extrapolation (%AUCex) will be calculated as: %AUCex = [AUC(0-inf) – AUC(0-t)] / AUC(0-inf) x 100
Cmax	Maximum observed concentration will be obtained directly from the concentration-time data.
Tmax	Time to first occurrence of Cmax will be obtained directly from the concentration-time data.
t½	Apparent terminal phase half-life will be calculated as: t½ = In2 / lambda_z
Tlast	The time of the last measurable (positive) concentration.
lambda_z	The first order rate constant associated with the terminal (log-linear) portion of the curve.
lambda_z lower	The lower limit on time for values to be included in the calculation of lambda_z.
lambda_z upper	The upper limit on time for values to be included in the calculation of lambda_z.
#pts	The number of time points used in computing lambda_z.
R-square	Square of the correlation coefficient.
CL/F	Apparent clearance following oral dosing will be calculated as: CL/F = Dose / AUC (0-inf)
Vd/F	Apparent volume of distribution following oral dosing will be calculated as: Vd/F = Dose / lambda_z * AUC(0-inf)

NOTES:

- Additional parameters may be included as required.
- Lambda_z is the terminal phase rate constant.
- Ct is the last observed quantifiable concentration.

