10.1. Sample Size Determination

10.1.1. Sample Size Assumptions

The sample size is based on feasibility where sufficient subjects will be enrolled into the study to support the inclusion of 12 evaluable subjects for analysis and 6 subjects are assigned to each group (Japanese or Caucasian).

Between-subject estimates of variability of the PK endpoints C_{max} and AUC(0-inf) of Pyrimethamine are estimated to be 18.1% (coefficient of variance, CV%) and 44.6% (CV%), respectively (based on Japanese PK data reported by [Otomo H, et al. 1985](#)). Based on these variability estimates, and a sample size of 6 (active treatment per group), the upper and lower bounds of 95% CI will be approximately 20.7% for C_{max} and 56.4% for AUC(0-inf) respectively. For instance, the 95% CI of geometric mean will be 331.3-483.0 if the geometric mean of C_{max} (ug/mL) is 400, and the 95% CI of geometric mean will be 25.6-62.5 if the geometric mean of AUC(0-inf) (ug·hr/mL) is 40.

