10.3.2. Pharmacokinetic Analyses

All PK analyses will be described in the PK Population. The details of the PK analysis will be provided in the RAP.

Statistical Analysis Methods
Pyrimethamine concentrations
Plasma concentrations of Pyrimethamine at each assessment point will be listed to prepare figures showing individual concentration-time profiles on both linear and semi-log scales. In addition, the mean and median plasma concentrations at each assessment point will be calculated from concentration data of individual subjects to prepare figures showing mean and median plasma concentration-time profiles on both linear and semi-log scales by group.
Pyrimethamine PK parameters
The PK parameters [i.e., C _{max} , AUC(0-t), AUC(0-inf), AUC(0-24), t _{max} , t _{1/2} , CL/F, V _d /F] will be calculated by non-compartmental analysis from plasma Pyrimethamine concentration-time data using Phoenix WinNonlin (version 6.3 or higher), as data permit. Calculations will be based on the actual sampling times recorded during the study. All derived parameters will be listed and summarized descriptively by each group.

Others

An exploratory analysis will be performed using PK parameter plots in order to assess the results in the Japanese and Caucasian subjects.

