Continuous Data	Refer to IDSL Statistical Principle 6.06.1		
Categorical Data	N, n, frequency, %		
Reporting of Pharm	acokinetic Concentration Data		
Descriptive	Refer to IDSL Statistical Principle 6.06.1		
Summary Statistics	Assign zero to NQ values (Refer to GUI_51487 for further details)		
Reporting of Pharm	acokinetic Parameters		
Descriptive Summary Statistics (Log Transformed)	N, n, geometric mean, 95% CI of geometric mean, standard deviation (SD) of logged data and between geometric coefficient of variation (CVb (%)) will be reported. $ \text{CV}_b \text{ (\%)} = \sqrt{\left(\text{exp}(\text{SD}^2) - 1\right) * 100} $ (SD = SD of log transformed data)		
Parameters Not Being Log Transformed	Tmax		
Parameters Not Being Summarised	The following PK parameters will not be summarised but listed: %AUCex, Tlast, lambda_z, lambda_z_lower, lambda_z_upper, #pts, R2		
Graphical Displays			
Refer to IDSL Statistical Principals 7.01 to 7.13.			

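### Does the missing bracket in the SAP's Vd/F formula put a primary pharmacokinetic parameter at risk?

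*SAP*

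**What the plan says.** The protocol names Vd/F among the eight parameters of the primary endpoint for Japanese subjects and of the matching secondary endpoint for Caucasian subjects (Protocol Section 4). It gives no formula and leaves the detail to the SAP. Protocol Section 10.3.2 says the parameters "will be calculated by non-compartmental analysis from plasma Pyrimethamine concentration-time data using Phoenix WinNonlin (version 6.3 or higher), as data permit".

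SAP Section 8.3.1 repeats the choice of tool: "The pharmacokinetic parameters will be calculated by non-compartmental analysis using Phoenix WinNonlin (version 6.3 or higher"). Three rows of its Table 7 matter here:

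- Vd/F: "Apparent volume of distribution following oral dosing will be calculated as: Vd/F = Dose / lambda_z * AUC(0-inf")
- CL/F, the row directly above: "Apparent clearance following oral dosing will be calculated as: CL/F = Dose / AUC (0-inf")
- %AUCex: "AUCex = [AUC(0-inf) – AUC(0-t)] / AUC(0-inf) x 100"

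Several of these quotes stop one character short of the bracket that closes AUC(0-inf). That bracket is present in the text. The one in question is a further pair enclosing the product of lambda_z and AUC(0-inf).

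On reporting, SAP Section 10.4.3 states: "The following PK parameters will not be summarised but listed: %AUCex, Tlast, lambda_z", followed by the other lambda_z diagnostics. Vd/F is not on that list, so under SAP Section 8.3.2 it is summarised on both the raw and the log scale, with 95% confidence intervals.

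**The concern.** Division and multiplication have equal precedence, so the printed Vd/F line, taken in standard order, means Dose divided by lambda_z, then multiplied by AUC(0-inf). That puts the AUC on the wrong side of the fraction.

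A charitable convention, that everything after the slash is the denominator, repairs the Vd/F row but breaks the %AUCex row, which is correct only when read from left to right. No single reading convention makes both rows right.

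The parameter is in the primary endpoint, and this line is its only stated derivation. If someone programmed or checked Vd/F from the line as it stands, the values would be wrong in size and units and would move the wrong way with exposure. Even with correct reported values, the stated derivation would not match them.

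**Working it through.** Neither document states a value for Vd/F, so there is no figure to reproduce. The check is whether the rest of Table 7 settles the meaning, and how far apart the two readings lie.

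**Inputs**

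- Dose 50 mg (Protocol Section 4).
- Half-life 106.9 h in Japanese subjects (Protocol Section 3.2) and about 90 h in non-Japanese subjects (Protocol Section 5.4). These are background values from the sulfadoxine combination tablet.
- AUC(0-inf) of 40 ug·hr/mL, equal to 40 mg·h/L. This is the worked example in Protocol Section 10.1.1, where "the 95% CI of geometric mean will be 25.6-62.5 if the geometric mean of AUC(0-inf") is 40. It illustrates precision and is not a forecast.

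**Check on the AUC input.** With a CV of 44.6% and n = 6, the SD on the log scale is sqrt(ln(1 + 0.446²)) = 0.426. The half-width is 2.571 × 0.426 / sqrt(6) = 0.447, and exp(0.447) = 1.564. The interval is 40/1.564 to 40 × 1.564, or 25.6 to 62.5, as the protocol states.

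**Step 1: what Table 7 implies.** Its half-life row gives lambda_z = ln2 / t½, which is 0.6931/106.9 = 0.006484 per hour (0.007702 at 90 h). Its CL/F row, "CL/F = Dose / AUC (0-inf"), gives 50/40 = 1.25 L/h. An apparent volume is clearance divided by the terminal rate constant:

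Vd/F = (CL/F) / lambda_z = Dose / (lambda_z × AUC(0-inf)) = 1.25 / 0.006484 = 192.8 L (162.3 L at 90 h).

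**Step 2: units.** The intended form gives mg / (h⁻¹ × mg·h/L) = L. The literal form gives mg × h × mg·h/L = mg²·h²/L, which is not a volume.

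**Step 3: size of the gap.** The literal reading divided by the intended one is always AUC(0-inf) squared, whatever the dose or half-life.

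| AUC(0-inf), mg·h/L | CL/F, L/h | Intended Vd/F at 106.9 h, L | Intended Vd/F at 90 h, L | Literal reading at 106.9 h, mg²·h²/L | Literal / intended |
|---|---|---|---|---|---|
| 25.6 | 1.953 | 301.2 | 253.6 | 197,407 | 655 |
| 40 | 1.25 | 192.8 | 162.3 | 308,448 | 1,600 |
| 62.5 | 0.80 | 123.4 | 103.9 | 481,950 | 3,906 |

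From the lowest to the highest AUC the intended form falls by a factor of 123.4/301.2 = 0.41. The literal form rises by 62.5/25.6 = 2.44. The gap also depends on the unit: with AUC in ng·h/mL (40,000) it would be 40,000² = 1.6 billion. It is therefore not an effect size for this trial.

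**Step 4: the %AUCex row.** Take illustrative values of 40 for AUC(0-inf) and 36 for AUC(0-t). Left to right the row gives (40 − 36)/40 × 100 = 10%. With everything after the slash as denominator it gives 4/(40 × 100) = 0.001. The table is indeed loose in its notation, but each row has only one sensible meaning.

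**Step 5: what uses the line.** Vd/F comes from WinNonlin, and SAP Section 8.3.1 places the derivation with, or under, the sponsor's clinical pharmacology group. The precision statements in Protocol Sections 10.1.1 and 10.1.2 cover only Cmax and AUC. The group plots in SAP Section 8.3.2 use AUC(0-t), AUC(0-inf), Cmax and half-life. No hypothesis is tested. Vd/F appears only in descriptive summaries and listings.

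**The case for a change.** The best case for a correction is that an SAP should state correctly how a primary parameter is derived, that an expert's ability to recover the meaning is not the same as a correct specification, and that the repair is one pair of brackets with no amendment and no new data. The protocol sends the reader to the SAP for exactly this detail.

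The factual part stands: the line as read is wrong in strict order, and there is no other formula. Two things weaken the rest.

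First, the harm needs someone to compute Vd/F from Table 7, and neither document describes such a step. If someone did, the units and the CL/F row would expose the mistake at once, and the listed CL/F and lambda_z allow each subject's value to be checked by one division.

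Second, the bracket may be present in the source. Brackets survive in the %AUCex row, which argues against a loss. But the text of this SAP is damaged elsewhere: the BMI formula in Section 10.5.2 lacks a closing bracket, a study-day formula in Section 10.5.1 lacks its minus sign, and the exponential in the AUC(0-24) row of Table 7 is garbled. Neither explanation can be proved from the text alone.

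**Conclusion.** No change to the plan follows. This is a clerical slip in notation, or a bracket lost in reading the PDF. The method is not in error. The meaning is fixed by the CL/F row and by the name of the quantity, and the values come from software. The contrast between 192.8 L and about 308,000 in non-volume units shows how conspicuous a literal use would be. It does not measure any effect on the trial, which is expected to be nil for every estimate, interval and conclusion.

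This rests on two assumptions: that WinNonlin's non-compartmental output for Vd/F is the apparent volume named in Table 7, and that nobody overwrites it with a calculation from the printed line. Both are what the documents describe. The AUC and half-life values are illustrative; the finding that the two readings differ by AUC(0-inf) squared does not depend on them.
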